### 7.3.2 Secondary analyses

As sensitivity analysis, the ANOVA performed as primary analysis will be repeated with subject as fixed effect instead of random effect. The results will be presented in the same manner as for primary analyses.

The following descriptive statistics will be calculated for primary and secondary PK parameters and for further endpoints: N, arithmetic mean, standard deviation, minimum, median, maximum, arithmetic coefficient of variation, geometric mean, and geometric coefficient of variation. The data format for descriptive statistics of concentrations will be

Proprietary confidential information © 2017 Boehringer Ingelheim International GmbH or one or more of its affiliated companies

identical with the data format of the respective concentrations. The descriptive statistics of PK parameters will be calculated using the individual values with the number of decimal places as provided by the evaluation program. Then the individual values as well as the descriptive statistics will be reported with 3 significant digits in the clinical trial report.

### **7.3.3 Safety analyses**

Safety will be assessed for the endpoints listed in [Section 5.2.1](#). All treated subjects (that is, all subjects who received at least one dose of study drug), will be included in the safety evaluation. Safety analyses will be descriptive in nature and will be based on BI standards.

The analyses will be done by 'treatment at onset'.

Treatments will be compared in a descriptive way. Tabulations of frequencies/proportions will be used for the evaluation of categorical (qualitative) data, and tabulations of descriptive statistics will be used to analyse continuous (quantitative) data.

Measurements (such as ECG, vital signs, or laboratory parameters) or AEs will be assigned to treatments (see [Section 4.1](#)) based on the actual treatment at the planned time of the measurement or on the recorded time of AE onset (concept of treatment emergent AEs).

Therefore, measurements planned or AEs recorded prior to first intake of trial medication will be assigned to 'screening', those between first trial medication intake until end of the residual effect period (see [5.2.2.2](#)) will be assigned to the treatment period. Events after the residual effect period but prior to end of trial examination will be summarized as 'follow-up'. These assignments including the corresponding time intervals will be defined in detail in the TSAP.

Adverse events will be coded using the Medical Dictionary for Regulatory Activities (MedDRA). Frequency, intensity and causal relationship of AEs will be tabulated by treatment, primary system organ class and preferred term. SAEs and other significant AEs (according to ICH E3), and AESIs will be listed separately (see [Section 5.2.2.1](#)).

Laboratory data will be compared to their reference ranges. Values outside the reference range will be flagged. Additionally, differences from baseline (Day 1 of period 1) will be evaluated.

For vital signs, the differences from baseline will be evaluated.

Relevant ECG findings will be reported as AEs.

### **7.3.4 Interim analyses**

No interim analysis is planned.

### **7.3.5 Pharmacokinetic analyses**

For the analysis of pharmacokinetic parameters please refer to [Section 7.3.1](#).

## **7.4 HANDLING OF MISSING DATA**

### **7.4.1 Safety**

With respect to safety evaluations, it is not planned to impute missing values.

### **7.4.2 Plasma drug concentration - time profiles**

Handling of missing PK data will be performed according to the relevant Corporate Procedure of the Sponsor ([001-MCS-36-472](#)).

Drug concentration data identified with NOS (no sample available), NOR (no valid result), NOA (not analyzed), or BLQ (below the lower limit of quantification), will be displayed as such and not replaced by zero at any time point (this rule also applies also to the lag phase, including the predose values).

### **7.4.3 Pharmacokinetic parameters**

Handling of missing PK data will be performed according to the relevant SOP of the Sponsor (001-MCS-36-472).

For the non-compartmental analysis, concentration data identified with NOS, NOR or NOA will generally not be considered. Concentration values in the lag phase identified as BLQ or NOP will be set to zero. All other BLQ values of the profile will be ignored. The lag phase is defined as the period between time zero and the first time point with a concentration above the quantification limit.

## **7.5 RANDOMISATION**

Randomization is not applicable in this open-label and single group clinical study. All subjects will receive the same treatment. (see [Section 4.1.2](#) for details of allocation of subject numbers to subjects).

## **7.6 DETERMINATION OF SAMPLE SIZE**

It is planned to enter a total of 16 subjects into the trial, because this sample size is considered sufficient to achieve the aims of this exploratory trial.

All calculations were performed as described by Kupper and Hafner [[R12-0972](#)] using R Version 3.2.2.

## **8. INFORMED CONSENT, DATA PROTECTION, TRIAL RECORDS**

The trial will be carried out in compliance with the protocol, the principles laid down in the Declaration of Helsinki, in accordance with the ICH Harmonised Tripartite Guideline for Good Clinical Practice (GCP) and relevant BI SOPs.

The investigator should inform the sponsor immediately of any urgent safety measures taken to protect the study subjects against any immediate hazard, and also of any serious breaches of the protocol or of ICH GCP.

The rights of the investigator and of the sponsor with regard to publication of the results of this trial are described in a separate agreement between the investigator or the trial site and the sponsor. As a general rule, no trial results should be published prior to finalisation of the CTR.

Insurance Coverage: The certificate of insurance cover is made available to the Investigator and the subjects, and is stored in the ISF.

### **8.1 STUDY APPROVAL, SUBJECT INFORMATION, AND INFORMED CONSENT**

This trial will be initiated only after all required legal documentation has been reviewed and approved by the respective Institutional Review Board (IRB) / Independent Ethics Committee (IEC) and competent authority (CA) according to national and international regulations. The same applies for the implementation of changes introduced by amendments.

Prior to a subject's participation in the trial, written informed consent must be obtained from each subject (or the subject's legally accepted representative) according to ICH GCP and to the regulatory and legal requirements of the participating country. Each signature must be personally dated by each signatory and the informed consent and any additional subject information form are to be retained by the investigator as part of the trial records. A copy of the signed and dated written informed consent and any additional subject information must be given to each subject or the subject's legally accepted representative.

The subject must be informed that his/her personal trial-related data will be used by Boehringer Ingelheim in accordance with the local data protection law. The level of disclosure must also be explained to the subject.

The subject must be informed that his or her medical records may be examined by authorised monitors (Clinical Monitor Local/Clinical Research Associate) or Clinical Quality Assurance auditors appointed by Boehringer Ingelheim, by appropriate IRB/IEC members, and by inspectors from regulatory authorities.

### **8.2 DATA QUALITY ASSURANCE**

A quality assurance audit/inspection of this trial may be conducted by the sponsor or sponsor's designees, by IRBs/IECs, or by regulatory authorities. The quality assurance auditor will have access to all medical records, the investigator's trial-related files and correspondence, and the informed consent documentation of this clinical trial.

The data management procedures to ensure the quality of the data are described in detail in the trial data management and analysis plan (TDMAP) available in the CTMF.

### **8.3 RECORDS**

CRFs for individual subjects will be provided by the sponsor. For drug accountability, refer to [Section 4.1.8.](#)

#### **8.3.1 Source documents**

Source documents provide evidence for the existence of the subject and substantiate the integrity of the data collected. Source documents are filed at the investigator's site.

All data reported in the CRFs must be consistent with the source data or the discrepancies must be explained.

The investigator may need to request previous medical records or transfer records, depending on the trial.

#### **8.3.2 Direct access to source data and documents**

The investigator/institution will permit trial-related monitoring, audits, IRB/IEC review and regulatory inspection, providing direct access to all related source data/documents. CRFs and all source documents, including progress notes (if applicable) and copies of laboratory and medical test results must be available at all times for review by the sponsor's clinical trial monitor, auditor and inspection by health authorities (e.g. FDA). The Clinical Research Associate/on site monitor and auditor may review all CRFs, and written informed consents. The accuracy of the data will be verified by reviewing the documents described in Section 8.3.1.

#### **8.3.3 Storage period of records**

##### Trial site:

The trial site must retain the source and essential documents (including ISF) according to the national or local requirements (whatever is longer) valid at the time of the end of the trial.

##### Sponsor:

The sponsor must retain the essential documents according to the sponsor's SOPs.

### **8.4 EXPEDITED REPORTING OF ADVERSE EVENTS**

BI is responsible to fulfil their legal regulatory reporting obligation and in accordance to the requirements defined in this CTP.

## **10. APPENDICES**

Not applicable.

Proprietary confidential information © 2017 Boehringer Ingelheim International GmbH or one or more of its affiliated companies

## 11. DESCRIPTION OF GLOBAL AMENDMENT(S)

Number of global amendment	1
Date of CTP revision	14 Jul 2017
EudraCT number	
BI Trial number	1289-0040
BI Investigational Product(s)	BI 409306
Title of protocol	A study to investigate the pharmacokinetic drug-drug interaction following oral administration of ethinylestradiol/levonorgestrel (Microgynon®) and BI 409306 in healthy Korean premenopausal female subjects (an open-label, two-period, fixed-sequence study)
To be implemented only after approval of the IRB / IEC / Competent Authorities	
To be implemented immediately in order to eliminate hazard – IRB / IEC / Competent Authority to be notified of change with request for approval	
Can be implemented without IRB / IEC / Competent Authority approval as changes involve logistical or administrative aspects only	
Section to be changed	

1. Flow Chart

2. Section 1.2.1

3. Section 3.3.4.1

4. Section 4.1.4

5. Section 5.2.3

6. Section 5.5.3.1

7. Section 5.5.2.2

8. Section 7.3.1

Description of change	

1. Remove 'Assignment of medication numbers' on Day 1 Change '684:00' and '21:00' → '686:00' and '23:00'

2. Change 'visual blurred' → 'vision blurred'

3. Remove 'The only exception to this rule is when the subject had an AESI and/or SAE'

Proprietary confidential information © 2017 Boehringer Ingelheim International GmbH or one or more of its affiliated companies

Number of global amendment		1
		
that the investigator considers related to the screening procedure.'
 
Change 'first administration of trial medication' → 'first administration of trial medication in run-in period'
 

4. Change 'No Microgynon® tablets are to be taken in the last 6 days of the run-in period.' → 'No Microgynon® tablets are to be taken in the last 7 days of the run-in period.'

5. Change 'Plasma glucose' → 'Serum glucose' Add punctuation and 'Anti-cardiolipin antibody' in thrombosis panel

6. Delete the name of analysts

7. Change 'The second aliquot will be shipped after the bioanalyst has acknowledged safe arrival of the first and second aliquots.' → 'The second aliquot will be shipped after the bioanalyst has acknowledged safe arrival of the first aliquot.'

8. Change 'plasma and urine' → 'plasma'

Rationale for change		

1. Correction

2. Correction

3. To avoid confliction with section 5.2.2.2

4. Correction

5. To clarify the safety lab test

6. Correction

7. To avoid further amendment

8. Correction

2. LIST OF ABBREVIATIONS

Term	Definition / description
ADS	Analysis data set
AE	Adverse event
BMI	Body mass index
CTP	Clinical trial protocol
CTR	Clinical trial report
DBL	Data base lock
ES	Entered set
ICH	International Conference on Harmonisation
MedDRA	Medical Dictionary for Regulatory Activities
O * C	Oracle ClinicalTM
PK	Pharmacokinetic
PKS	Pharmacokinetic set
PV	Protocol violation
RAGe	Report Appendix Generator system
REP	Residual effect period
RPM	Report planning meeting
SAE	Serious adverse event
SD	Standard deviation
TS	Treated set
TSAP	Trial statistical analysis plan

3. INTRODUCTION

As per International Conference on Harmonisation (ICH) E9 ([1](#)), the purpose of this document is to provide a more technical and detailed elaboration of the principal features of the analysis described in the protocol, and to include detailed procedures for executing the statistical analysis of the primary and secondary variables and other data.

This trial statistical analysis plan (TSAP) assumes familiarity with the Clinical Trial Protocol (CTP), including Protocol Amendments. In particular, the TSAP is based on the planned analysis specification as written in CTP Section 7 “Statistical Methods and Determination of Sample Size”. Therefore, TSAP readers may consult the CTP for more background information on the study, e.g., on study objectives, study design and population, treatments, definition of measurements and variables, planning of sample size, randomisation.

Study data will be stored in a trial database within the Oracle ClinicalTM (O*C) system.

Pharmacokinetic (PK) parameters will be calculated using Phoenix WinNonlinTM software (version 6.3, Certara USA Inc., Princeton, NJ, USA).

The statistical analyses will be performed within the validated working environment CARE, including SASTM (current Version 9.4, by SAS Institute Inc., Cary, NC, USA), and a number of SASTM-based tools (e.g., macros for the analyses of adverse event (AE) data or laboratory data; Report Appendix Generator system (RAGe) for compilation/formatting of the clinical trial report (CTR) appendices).

4. CHANGES IN THE PLANNED ANALYSIS OF THE STUDY

There will be no changes in the planned analysis of the study.

5. ENDPOINT(S)

5.1 PRIMARY ENDPOINT(S)

Primary PK endpoints as defined in Section 5.5.1.1 of the CTP:

The following primary endpoints will be determined for BI 409306

- AUC_{0-tz} (area under the concentration-time curve of the analyte in plasma over the time interval from 0 to the last quantifiable data point)
- C_{max} (maximum measured concentration of the analyte in plasma)

The following primary endpoints will be determined for ethinylestradiol and levonorgestrel:

- $AUC_{0-24,ss}$ (area under the concentration-time curve of the analyte in plasma over the time interval from 0 to the last quantifiable data point)
- $C_{max,ss}$ (maximum measured concentration of the analyte in plasma)

5.2 SECONDARY ENDPOINT(S)

5.2.1 Key secondary endpoint(s)

There are no key secondary endpoints in this trial.

5.2.2 Secondary endpoint(s)

Section 5.5.1.2 of the CTP:

The following secondary endpoints will be evaluated for BI 409306:

- $AUC_{0-\infty}$ (area under the concentration-time curve of the analyte in plasma over the time interval from 0 extrapolated to infinity)

6. GENERAL ANALYSIS DEFINITIONS

6.1 TREATMENT(S)

For basic study information on investigational products, assignments of treatment, and selection of doses, please see CTP, Sections 3 and 4. For details of dosage and formulation see Table 6.1: 1 below.

Table 6.1: 1 Labels for treatments for use in the CTR

Treatment	Substance	Formulation	Unit strength	Dosage	Short label
R1 (Reference 1)	BI 409306	Film coated tablet	25 mg	1 tablet on Day 29	BI
T1 (Test 1)	BI 409306 Microgynon®	Film coated tablet Coated tablet	25 mg 0.03 mg EE / 0.15 mg LNG	1 tablet on Day 18	BI+Microgynon®
R2 (Reference 2)	Microgynon®	Coated tablet	0.03 mg EE / 0.15 mg LNG	1 tablet on Day 17	Microgynon®
T2 (Test 2)	Microgynon® BI 409306	Coated tablet Film coated tablet	0.03 mg EE / 0.15 mg LNG 25 mg	1 tablet on Day 18	BI+Microgynon®

The following separate study phases will be defined for the analyses of AEs:

- Screening (ranging from day of informed consent until first administration of study drug)
- Microgynon® treatment (ranging from the time of first intake of Microgynon® until the time of first administration of BI 409306 or last intake of Microgynon® + Microgynon® REP (10 days), whatever occurs earlier)
- BI 409306 + Microgynon® treatment (ranging from the first administration of BI 409306 + Microgynon® until end of Microgynon® REP (10 days))
- BI 409306 treatment
- Follow up BI 409306 treatment

The residual effect period (REP) for BI 409306, when measurable drug levels or PD effects are still likely to be present, The REP for Microgynon® is considered to be 10 days.

Displays of AEs will be presented separately for the following treatments during on treatment phase:

- BI 409306, tablet, qd (labelled "BI")
- Microgynon®, tablet, qd (labelled "Microgynon")
- BI 409306, tablet, qd + Microgynon®, tablet, qd (labelled "BI + Microgynon")

Two types of AE displays will be provided in the report:

A) Section 15.3 and Appendix 16.1.9.2.8 (for ClinicalTrials.gov) of the CTR displays:

In these displays, the on treatment phase will be analysed (labelled with the name of the study treatment (short label)). Screening and Follow-up BI will not be included in this analysis.

The following total will be provided in addition (Section 15.3 only):

- a total over all on treatment phases involving BI ("Total BI")
- a total over all on treatment phases included in this analysis ("Total on treatment")

B) Section 15.4 and Appendix 16.1.9.2.8 (except for ClinicalTrials.gov) of the CTR displays:

- Screening
- On treatment (labelled with the name of the study treatment (short label))
- Follow-up BI (labelled "FU BI")

In Section 16.1.9.2.8 AE tables, the following totals will be provided in addition:

- a total over all study phases ("Total")

Tables of vital signs and laboratory values will present results by the following separate study phases which will be defined for the analyses of vital signs and laboratory values:

- Screening (ranging from day of informed consent until first administration of study drug)
- Microgynon® treatment (ranging from first intake of Microgynon® until first administration of BI 409306 or last intake of Microgynon® + Microgynon® REP (10 days), whatever occurs earlier)
- BI 409306 + Microgynon® treatment (ranging from first administration of BI 409306 + Microgynon® until administration of BI 409306 +)
- Microgynon® treatment (ranging from end of until last intake of Microgynon® + Microgynon® REP (10 days))
- BI 409306 treatment (ranging from first administration of BI 409306 alone until EOT or last intake of BI 409306 + whatever occurs earlier)

- Follow up BI 409306 treatment (ranging from end of last BI 409306 treatment +

For detailed information on the handling of the treatments in the O*C views refer to Technical TSAP analysis data set (ADS) plan.

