Duration of treatment: Run-in period (Day -49/-28 to Day -8) Microgynon® QD for 21-42 days (until Day -8) (depending on individual stage of menstrual cycle)				
Treatment period Days 1 to 17: Microgynon® QD for 17 days (R2 on Day 17) Day 18: BI 409306 + Microgynon® (T1 and T2) Days 19 to 21: Microgynon® QD for 3 days Day 29: BI 409306 (R1)				
Treatments: BI 409306 as victim (part 1): Reference 1 (R1): 1 tablet BI 409306 on Day 29.  Test 1 (T1): 1 tablet BI 409306 together with 1 tablet Microgynon® QD on Day 18.				
Microgynon® as victim (part 2): Reference 2 (R2): 1 tablet Microgynon® QD on Day 17  Test 2 (T2) : 1 tablet Microgynon® QD together with 1 tablet BI 409306 on Day 18				
Criteria for pharmacokinetics: Primary endpoints: (part 1) BI 409306 as victim AUC 0-tz and C max of BI 409306 in plasma for T1 compared with R1  (part 2) Microgynon® as victim AUC 0-24,ss and C max,ss of EE in plasma for T2 compared with R2 AUC 0-24,ss and C max,ss of LNG in plasma for T2 compared with R2  Secondary endpoint: (part 1) BI 409306 as victim AUC 0-∞ of BI 409306 in plasma for T1 compared with R1				

Proprietary confidential information © 2017 Boehringer Ingelheim International GmbH or one or more of its affiliated companies

Name of company: Boehringer Ingelheim		Tabulated Trial Protocol		
Name of finished product: Not applicable				
Name of active ingredient: BI 409306				
Protocol date: 30 Mar 2017	Trial number: 1289-0040		Revision date: 14 Jul 2017	
Criteria for safety: Adverse events (AEs) including clinically relevant findings from the physical examination, safety laboratory tests, 12-lead electrocardiogram (ECG), vital signs (blood pressure [BP], pulse rate [PR])				

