##### **Run-in-period**

All subjects will undergo a run-in period (Visit 2) that starts between Day -49 and Day -28. In this period, the subjects will take one tablet of Microgynon® daily (for 21-42 days) until Day -8. In the last 7 days of the run-in period (Day -7 to Day -1) no treatment will be given in order to induce withdrawal bleeding. The next day will be Day 1. Subjects who have already been using oral contraceptives before the study will start the run-in period after the usual tablet-free interval of 7 days. Subjects who have been using hormonal contraceptive vaginal rings before the study will start the run-in-period after the usual hormone-free interval of 7 days.

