7.7 EXTENT OF EXPOSURE

Only listing is planned for this section of the report.

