7.8.1 Adverse events

AEs will be coded with the most recent version of MedDRA. The analyses of AEs will be descriptive in nature. All analyses of AEs will be based on the number of subjects with AEs and not on the number of AEs.

For analysis multiple AE occurrence data on the case report form (CRF) will be collapsed into one AE provided that all of the following applies:

- All AE attributes are identical (lower level term, intensity, action taken, therapy required, seriousness, reason for seriousness, relationship, outcome, AE of special interest).
- The occurrences were time-overlapping or time-adjacent (time-adjacency of 2 occurrences is given if the second occurrence started within one hour after end of the first occurrence).

For further details on summarisation of AE data, please refer to ([5](#), [8](#)).

Section 5.2.2.1 of the CTP:

The following are considered as AESIs in this trial:

- *Hepatic injury, as defined by the following alterations of hepatic laboratory parameters:*
 - *an elevation of AST and/or ALT ≥ 3 -fold ULN combined with an elevation of total bilirubin ≥ 2 -fold ULN measured in the same blood sample, and/or*
 - *marked peak aminotransferase (ALT, and/or AST) elevations ≥ 10 fold ULN*

The analysis of AEs will be based on the concept of treatment emergent AEs.

Section 5.2.2.2 of the CTP:

The REP for Microgynon is defined as 10 days after the last administration of Microgynon®.

Therefore, all AEs which occurred through the treatment phase and throughout the REP will be considered as on treatment; please see Section 7.3.3 of CTP. Events which occurred after the REP will be considered as post treatment events.

For details on the treatment definition, see [Section 6.1](#).

According to ICH E3 ([9](#)), AEs classified as ‘other significant’ needs to be reported and will include those non-serious with

- (i) ‘action taken = discontinuation’ or ‘action taken = reduced’, or
- (ii) marked haematological and other lab abnormalities or lead to significant concomitant therapy as identified by the Clinical Monitor/Investigator at a RPM/database lock (DBL) meeting.

An overall summary of AEs will be presented.

The frequency of subjects with AEs will be summarised by treatment, primary system organ class and preferred term (MedDRA levels to be displayed in the tables).

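### The Microgynon AE column spans 45 to 66 days against 11 to 13 for the combination and at most 4 to 6 for BI 409306 alone, so crude subject percentages are not comparable between treatments

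*SAP*

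**What the plan says.** Protocol 7.1.1 makes safety and tolerability an additional objective. Protocol 7.3.3 states "Treatments will be compared in a descriptive way", assigns AEs to treatment by time of onset, and leaves the exact time intervals to the SAP.

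SAP 6.1 sets those intervals for AEs:

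- **Microgynon:** "Microgynon® treatment (ranging from the time of first intake of Microgynon® until the time of first administration of BI 409306", or to last intake plus the 10-day residual effect period (REP) if that is earlier.
- **BI + Microgynon:** from the first combined dose to the end of the Microgynon REP.
- **BI 409306 alone:** listed without a visible range. For laboratory values and vital signs it ends at the end-of-trial visit at the latest.

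On the start of Microgynon intake, Protocol 3.1 says "All subjects will undergo a run-in period (Visit 2) that starts between Day -49 and Day -28".

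For the displays, SAP 7.8.1 says "All analyses of AEs will be based on the number of subjects with AEs and not on the number of AEs". SAP 7 bases percentages on all subjects in the analysis set. On exposure, SAP 7.7 says "Only listing is planned for this section of the report". No person-time summary appears.

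**The concern.** The chance that a subject has at least one AE in a phase grows with the length of the phase. Three columns of very different length, shown side by side as subject percentages, therefore mix treatment with duration. The direction favours the investigational product, because the contraceptive-alone reference column is by far the longest.

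The pooling also works against the design. Protocol 3.2 uses the run-in to limit the effect of adapting to a new contraceptive before the study periods begin. SAP 6.1 puts that adaptation time, and the week meant to induce withdrawal bleeding, back into the reference column. The run-in also differs between subjects by up to 21 days (49 − 28).

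At stake is whether a reader of the clinical trial report can tell from the AE tables if adding BI 409306 changes tolerability.

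**Working it through.** **Inputs from the documents**

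- Run-in starts between Day -49 and Day -28 (Protocol 3.1).
- There is no Day 0: after Day -1, "The next day will be Day 1" (Protocol 3.1).
- First BI 409306 dose: Day 18, 408 h. Last Microgynon dose: Day 21, 480 h. BI 409306 alone: Day 29, 672 h (Flow Chart).
- Microgynon REP: 10 days, or 240 h (SAP 6.1).
- End of trial: Days 33 to 35 (Flow Chart).
- 16 subjects (Protocol 7.6).

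**Input that is assumed.** A constant daily AE risk *q*, the same in every phase, with equal detection. The documents give no AE rate, so a range is shown.

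**Check of the day count.** The synopsis gives "Microgynon® QD for 21-42 days (until Day -8". Day -28 to Day -8 inclusive is 28 − 8 + 1 = 21 days; Day -49 to Day -8 inclusive is 49 − 8 + 1 = 42 days. The stated range is reproduced.

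**Phase lengths**

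- Microgynon: 28 + 17 = 45 to 49 + 17 = 66 days. The 7 tablet-free days do not end the phase, because 7 is less than the 10-day REP.
- BI + Microgynon: (672 − 408)/24 = 11 days if cut at the Day 29 dose; (480 + 240 − 408)/24 = 13 days to the end of the REP.
- BI alone: 33 − 29 = 4 to 35 − 29 = 6 days, as a ceiling.

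The Microgynon phase is thus 45/13 = 3.5 to 66/11 = 6 times as long as the combination phase, and at least 45/6 = 7.5 to 66/4 = 16.5 times as long as BI alone.

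**Expected percentage of subjects with an AE**, 1 − (1 − *q*)^days:

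| *q* per day | Microgynon (45–66 d) | BI + Microgynon (11–13 d) | BI alone (at most 4–6 d) |
|---|---|---|---|
| 0.1% | 4.4–6.4% | 1.1–1.3% | at most 0.4–0.6% |
| 0.5% | 20.2–28.2% | 5.4–6.3% | at most 2.0–3.0% |
| 1% | 36.4–48.5% | 10.5–12.2% | at most 3.9–5.9% |
| 2% | 59.7–73.6% | 19.9–23.1% | at most 7.8–11.4% |

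**Chance of seeing this order with 16 subjects.** Treating the two counts as independent binomials, the probability that strictly more subjects have an AE under Microgynon than under BI alone (45 vs 6 days to 66 vs 4 days) is:

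- 48 to 63% at 0.1% per day (ties 35 to 47%, reversed 2 to 5%)
- 91 to 98% at 0.5%
- 98 to 99.9% at 1%

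Against the combination (45 vs 13 to 66 vs 11 days) it is 93 to 99% at 1%.

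**Which rate removes the length effect?** Dividing subjects with an AE by *all* days in the phase does not. At 2% per day it gives 73.6/66 = 1.12 per 100 days over 66 days but 11.4/6 = 1.90 over 6 days, so the shorter phase now looks worse.

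Counting days only up to the first AE does remove it. Expected days at risk per subject are the sum of (1 − *q*)^j for j = 0 to d − 1, which equals [1 − (1 − *q*)^d]/*q*. Expected subjects with an AE divided by expected days at risk is then *q* for any length d.

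**Effect of the split alone.** Days 1 to 17 last 408/24 = 17 days. At 1% per day the expected percentage is 1 − 0.99^17 = 15.7%, much closer to the combination's 10.5 to 12.2% than the pooled 36.4 to 48.5% is.

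**The case against.** The strongest reply is that the consequence is small. Protocol 5.2.1 treats safety as descriptive, with no confirmatory analysis. The trial is exploratory with 16 subjects, and no visible rule acts on a difference in AE percentages. AE listings, tables of drug-related AEs and the exposure listing let a careful reader look at timing and attribution. This stands, and it limits the point to a cheap improvement.

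A second reply is that detection is unequal and may act the other way. In the run-in, phone contacts for AEs are at least weekly (Flow Chart, footnote 9). From Day 1 to Day 21 the Flow Chart schedules questioning every day, with repeated questioning on Days 17, 18 and 29. Under-reporting in the run-in could offset part of the duration effect, and the documents do not allow that part to be sized. Nor is questioning uniformly frequent after Day 1: none is scheduled on Days 22 to 27, inside the combination phase, although AEs are recorded throughout.

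A reader might infer more than the documents support in four ways:

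- *That Microgynon is certain to look worse.* This needs equal, constant risk and equal detection; at 0.1% per day a tie is about as likely at the shorter phase contrast.
- *That the BI-alone phase lasts 4 to 6 days.* That is only a ceiling. The BI 409306 REP is absent from the public text, which is not a defect of the plan, and a shorter phase would widen the gap.
- *That the Total BI and Total on treatment columns mislead in themselves.* They pool phases as labelled, and no mechanism makes them favour BI 409306.
- *That Days 7 to 17 are a fair length-matched reference for Days 18 to 28.* Both last 11 days, but Microgynon stops after Day 21. The contrast would mix the effect of BI 409306 with stopping the contraceptive and with the gap in questioning.

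**Conclusion.** The point holds as a matter of expectation. SAP 6.1 and 7.8.1 together set up a comparison in which the contraceptive-alone column is 3.5 to 6 times as long as the combination column and at least 7.5 to 16.5 times as long as the BI-alone column, with no time at risk shown. At equal daily risk and equal detection, Microgynon alone is expected to show the highest percentage of subjects with an AE: roughly 36 to 48% against 10 to 12% and at most 4 to 6%, if the risk is 1% per day.

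The phase lengths follow from the documents. The daily risk, its constancy and equal detection are assumptions, and sparser questioning in the run-in could reduce the gap. The effect is confined to the reading of descriptive AE tables.

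**What to change.** In SAP 6.1 and 7.8.1:

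1. Replace the single Microgynon AE column with two: run-in (first intake to Day -1) and Microgynon (Day 1 to the first BI 409306 dose).
2. Beside each percentage, show subject-days at risk, counted from the start of the phase and censored at the subject's first AE in that phase, and the resulting first-event rate per 100 subject-days. Each subject re-enters at risk when a new phase begins.
3. Add a footnote to the AE tables that raw percentages are not comparable across phases, because phase length and the frequency of AE questioning differ.

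The cost is SAP wording, one added phase column and the time-at-risk figures, all from dates already recorded. The rates will be imprecise: with 16 subjects and 1% per day, BI alone would be expected to yield 16 × 3.9% = 0.6 to 16 × 5.9% = 0.9 subjects with an AE. They also do not correct for unequal detection, which is why the footnote is needed as well.
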